### 1.2 OBJECTIVES AND ENDPOINTS

Table 1 - Objectives and endpoints

Objectives	Endpoints
Primary	
To evaluate the efficacy of dupilumab as assessed by the reduction at Week 24 in sinus opacification on computerized tomography (CT) scan in the dupilumab group only	

• Change from baseline to Week 24 in opacification of sinuses assessed by CT scan using the Lund-Mackay (LMK) score in the dupilumab group

Secondary	
To evaluate the efficacy of dupilumab as assessed by the reduction at Week 24 in sinus opacification on CT scan and sinus total symptom score (sTSS) compared to placebo	

• Change from baseline to Week 24 in opacification of sinuses assessed by CT scan using the LMK score

• Change from baseline to Week 24 in sTSS*

*\*Composite severity score consisting of nasal congestion, anterior/posterior rhinorrhea, facial*

Objectives	Endpoints
	pain/pressure items of the CRSsNP sinonasal symptom e-diary

 
• To evaluate the safety and tolerability of dupilumab in CRSsNP patients compared to placebo
 
	
 
• Incidence of treatment-emergent adverse events (TEAEs), of treatment-emergent serious AEs (TESAEs), and TEAEs leading to treatment discontinuation, abnormal laboratory values, and vital signs
 

 
• To evaluate the pharmacokinetics (PK) of dupilumab in CRSsNP patients
 
	
 
• Dupilumab concentration in serum
 

 
• Assessment of immunogenicity to dupilumab over time
 
	
 
• Assessment of immunogenicity to dupilumab as determined by the incidence, titer, and neutralizing antibody (NAb) status of treatment-emergent anti-drug antibody (ADA) response over time
 

Exploratory	

 
• [REDACTED]
 
	

 
• [REDACTED]
 
	

 
• [REDACTED]
 
	

 
• [REDACTED]
 
	

 
• [REDACTED]
 
	

 
• [REDACTED]
 
	

 
• [REDACTED]
 
	

 
• [REDACTED]
 
	

 
• [REDACTED]
 
	

 
• [REDACTED]
 
	

 
• [REDACTED]
 
	

 
• [REDACTED]
 
	

 
• [REDACTED]
 
	

 
• [REDACTED]
 
	

 
• [REDACTED]
 
	

 
• [REDACTED]
 
	

 
• [REDACTED]
 
	

 
• [REDACTED]
 
	

 
• [REDACTED]
 
	

 
• [REDACTED]
 
	

 
• [REDACTED]
 
	

 
• [REDACTED]
 
	

 
• [REDACTED]
 
	

 
• [REDACTED]
 
	

 
• [REDACTED]
 
	

 
• [REDACTED]
 
	

 
• [REDACTED]
 
	

 
• [REDACTED]
 
	

 
• [REDACTED]
 
	

 
• [REDACTED]
 
	

 
• [REDACTED]
 
	

 
• [REDACTED]
 
	

 
• [REDACTED]
 
	

 
• [REDACTED]
 
	

 
• [REDACTED]
 
	

 
• [REDACTED]
 
	

 
• [REDACTED]
 
	

 
• [REDACTED]
 
	

 
• [REDACTED]
 
	

 
• [REDACTED]
 
	

 
• [REDACTED]
 
	

 
• [REDACTED]
 
	

 
• [REDACTED]
 
	

 
• [REDACTED]
 
	

 
• [REDACTED]
 
	

 
• [REDACTED]
 
	

 
• [REDACTED]
 
	

 
• [REDACTED]
 
	

 
• [REDACTED]
 
	

 
• [REDACTED]
 
	

 
• [REDACTED]
 
	

 
• [REDACTED]
 
	

 
• [REDACTED]
 
	

 
• [REDACTED]
 
	

 
• [REDACTED]
 
	

 
• [REDACTED]
 
	

 
• [REDACTED]
 
	

 
• [REDACTED]
 
	

 
• [REDACTED]
 
	

 
• [REDACTED]
 
	

 
• [REDACTED]
 
	

 
• [REDACTED]
 
	

 
• [REDACTED]
 
	

 
• [REDACTED]
 
	

 
• [REDACTED]
 
	

 
• [REDACTED]
 
	

 
• [REDACTED]
 
	

 
• [REDACTED]
 
	

 
• [REDACTED]
 
	

 
• [REDACTED]
 
	

 
• [REDACTED]
 
	

 
• [REDACTED]
 
	

 
• [REDACTED]
 
	

 
• [REDACTED]
 
	

 
• [REDACTED]
 
	

 
• [REDACTED]
 
	

 
• [REDACTED]
 
	

 
• [REDACTED]
 
	

 
• [REDACTED]
 
	

 
• [REDACTED]
 
	

 
• [REDACTED]
 
	

 
• [REDACTED]
 
	

 
• [REDACTED]
 
	

 
• [REDACTED]
 
	

 
• [REDACTED]
 
	

 
• [REDACTED]
 
	

 
• [REDACTED]
 
	

 
• [REDACTED]
 
	

 
• [REDACTED]
 
	

 
• [REDACTED]
 
	

 
• [REDACTED]
 
	

 
• [REDACTED]
 
	

 
• [REDACTED]
 
	

 
• [REDACTED]
 
	

 
• [REDACTED]
 
	

 
• [REDACTED]
 
	

 
• [REDACTED]
 
	

 
• [REDACTED]
 
	

 
• [REDACTED]
 
	

 
• [REDACTED]
 
	

 
• [REDACTED]
 
	

 
• [REDACTED]
 
	

 
• [REDACTED]
 
	

 
• [REDACTED]
 
	

 
• [REDACTED]
 
	

 
• [REDACTED]
 
	

 
• [REDACTED]
 
	

 
• [REDACTED]
 
	

 
• [REDACTED]
 
	

 
• [REDACTED]
 
	

 
• [REDACTED]
 
	

 
• [REDACTED]
 
	

 
• [REDACTED]
 
	

 
• [REDACTED]
 
	

 
• [REDACTED]
 
	

 
• [REDACTED]
 
	

 
• [REDACTED]
 
	

 
• [REDACTED]
 
	

 
• [REDACTED]
 
	

 
• [REDACTED]
 
	

 
• [REDACTED]
 
	

 
• [REDACTED]
 
	

 
• [REDACTED]
 
	

 
• [REDACTED]
 
	

 
• [REDACTED]
 
	

 
• [REDACTED]
 
	

 
• [REDACTED]
 
	

 
• [REDACTED]
 
	

 
• [REDACTED]
 
	

 
• [REDACTED]
 
	

 
• [REDACTED]
 
	

 
• [REDACTED]
 
	

 
• [REDACTED]
 
	

 
• [REDACTED]
 
	

 
• [REDACTED]
 
	

 
• [REDACTED]
 
	

 
• [REDACTED]
 
	

 
• [REDACTED]
 
	

 
• [REDACTED]
 
	

 
• [REDACTED]
 
	

 
• [REDACTED]
 
	

 
• [REDACTED]
 
	

 
• [REDACTED]
 
	

 
• [REDACTED]
 
	

 
• [REDACTED]
 
	

 
• [REDACTED]
 
	

 
• [REDACTED]
 
	

 
• [REDACTED]
 
	

 
• [REDACTED]
 
	

 
• [REDACTED]
 
	

 
• [REDACTED]
 
	

 
• [REDACTED]
 
	

 
• [REDACTED]
 
	

 
• [REDACTED]
 
	

 
• [REDACTED]
 
	

 
• [REDACTED]
 
	

 
• [REDACTED]
 
	

 
• [REDACTED]
 
	

 
• [REDACTED]
 
	

 
• [REDACTED]
 
	

 
• [REDACTED]
 
	

 
• [REDACTED]
 
	

 
• [REDACTED]
 
	

 
• [REDACTED]
 
	

 
• [REDACTED]
 
	

Horizontal bar chart comparing 'Objectives' and 'Endpoints' across 10 categories. The 'Objectives' column shows mostly black bars, while the 'Endpoints' column shows mostly white bars with black outlines.

Category	Objectives	Endpoints
1	Black	White
2	Black	White
3	Black	White
4	Black	White
5	Black	White
6	Black	White
7	Black	White
8	Black	White
9	Black	White
10	Black	White

### 1.2.1 Estimands

Primary estimand defined for the primary endpoint is summarized in [Table 2](#). More details are provided in [Section 3.2.2](#).

**Table 2 - Summary of primary estimand for the primary endpoint**

Endpoint Category	Estimand			
	Endpoint	Population	Intercurrent event(s) handling strategy and missing data handling	Population-level summary
Primary objective: To evaluate the efficacy of dupilumab as assessed by the reduction at Week 24 in sinus opacification on computerized tomography (CT) scan in the dupilumab group only				
Primary endpoint	Change from baseline in LMK score at Week 24	ITT with screening blood eosinophil count $\geq 300$ cells/mm 	
The intercurrent events (IEs) will be handled as follows:
 
 
Undergoing sinonasal surgery for CRSsNP or taking systemic corticosteroids (SCS) for any reason prior to Week 24: data after the IE will be excluded from the analysis and the worst post-
 
	Descriptive statistics and 95% confidence interval (CI) in the dupilumab group will be provided.

Endpoint Category	Estimand			
	Endpoint	Population	Intercurrent event(s) handling strategy and missing data handling	Population-level summary
			
baseline value on or before the time of the IE will be used to assign the Week 24 value (WOCF). For participants with no post-baseline values, the baseline value will be used (composite strategy).
 

• Taking other prohibited/rescue medications: all data collected after use will be used in the analysis (treatment policy strategy).

• Discontinuing the study intervention: all data collected after discontinuation will be used in the analysis (treatment policy strategy).

 
Missing data will not be imputed.
	

## 2 ANALYSIS POPULATIONS

The following populations for analyses are defined. The primary population of the efficacy endpoints is the ITT population with screening blood eosinophil count  $\geq 300$  cells/mm $^3$ .

**Table 3 - Populations for analyses**

Population	Description
Screened	All participants who sign the informed consent form.
Randomized	The randomized population includes all participants with a treatment kit number allocated and recorded in the IRT database, and regardless of whether the treatment kit was used or not. Participants treated without being randomized will not be considered randomized and will not be included in any efficacy population.
Intent-to-treat (ITT)	All randomized participants analyzed according to the treatment group allocated by randomization regardless if treatment kit is used or not.
ITT with screening blood eosinophil count $\geq 300$ cells/mm $^3$	All randomized participants with screening blood eosinophil count $\geq 300$ cells/mm $^3$ analyzed according to the treatment group allocated by randomization regardless if treatment kit is used or not.
ITT with screening blood eosinophil count $< 300$ cells/mm $^3$	All randomized participants with screening blood eosinophil count $< 300$ cells/mm $^3$ analyzed according to the treatment group allocated by randomization regardless if treatment kit is used or not.
Safety	All participants randomly assigned to study intervention and who take at least 1 dose of study intervention. Participants will be analyzed according to the intervention they actually received. Randomized participants for whom it is unclear whether they took the study medication will be included in the safety population as randomized. For participants who accidentally receive different study intervention from the planned, the actual intervention allocation for as-treated analysis will be the dupilumab group.
Pharmacokinetic (PK)	The PK population includes all participants in the safety population with at least 1 non-missing result for functional dupilumab concentration in serum after the first dose of the study intervention. Participants will be analyzed according to the intervention actually received.
Anti-drug antibody (ADA)	ADA population includes all participants in the safety population who have at least 1 non-missing result in the ADA assay after the first dose of the study intervention. Participants will be analyzed according to the intervention actually received.
Population without trial impact (disruption) due to COVID-19	All randomized participants: 

without any critical or major deviation related to COVID-19

and who did not permanently discontinue treatment due to COVID-19

and who did not permanently discontinue study due to COVID-19.

Participants exposed to study intervention before or without being randomized will not be considered randomized and will not be included in any analysis population. The safety experience of these participants will be reported separately.

Randomized participants for whom it is unclear whether they took the study intervention will be considered as exposed and will be included in the safety population as randomized.

For any participant randomized more than once, only the data associated with the first randomization (except if the first randomization is done by error) will be used in any analysis

population. The safety experience associated with any later randomization will be reported separately.

For participants receiving more than one study intervention during the study, the intervention group for as-treated analyses will be the dupilumab group.

If >10% participants are impacted by the COVID-19 pandemic, additional summaries by COVID-19 subgroups will be provided. Participants impacted by the COVID-19 pandemic are defined as randomized participants with any critical or major deviation related to COVID-19 or who permanently discontinued study intervention or study due to COVID-19.

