## 4 STUDY DESIGN

### 4.1 OVERALL DESIGN

This is a Phase 2 multicenter study to evaluate the efficacy and safety of dupilumab, in participants with uncontrolled CRSsNP. This is a randomized, double-blind, placebo-controlled study in adult participants regardless of screening eosinophil count to evaluate the treatment effect of dupilumab on sinus opacification as assessed by the LMK sinus CT scan total score and to provide data on safety.

All participants (adults only) will enter a screening period (2 to 4 weeks), with a 24 to 52-week treatment period, followed by post-treatment follow-up (12 weeks).

Approximately 70 adult participants will be randomized 1:1 (approximately 35 participants per arm) into 2 treatment groups as follows:

- Arm A: Dupilumab 300 mg q2w,
- Arm B: Matching placebo.

Randomization will be stratified by screening blood eosinophil count ( $\geq 300$  cells/mm $^3$  or  $< 300$  cells/mm $^3$ ), background INCS use (yes or no) and region.

To ensure enrollment according to the intended distribution of screening blood eosinophil count, alerts will be built into the IRT to control the number of participants in each stratification group as follows:

- $\geq 300$  cells/mm $^3$ : approximately 15 participants per arm,
- $< 300$  cells/mm $^3$ : approximately 20 participants per arm.

*Note: The treatment will stop for all participants when the LPI has completed 24 weeks of treatment. Therefore, all participants following Amendment 02 will be treated for at least 24 weeks and the other participants (enrolled before Amendment 02) will have variable treatment period and may continue up to 52 weeks.*

In addition, in order to have an adequate number of participants with comorbid asthma, alerts will be built into the IRT to limit the number of participants without comorbid asthma to no more than 70% of the randomized population.

During the study, participants who report deterioration requiring medical/surgical intervention may come to the site for clinical evaluation. An unscheduled visit may be used for this purpose and, if necessary, the Investigator may consider one of the treatment alternatives described in [Section 6](#).

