**Table 5 - Populations for analyses**

Population	Description
Screened	All participants who sign the ICF.
Randomized	The randomized population includes all participants with a treatment kit number allocated and recorded in the IRT database, and regardless of whether the treatment kit was used or not. Participants treated without being randomized will not be considered randomized and will not be included in any efficacy population.
Intent-to-treat (ITT)	All randomized participants analyzed according to the treatment group allocated by randomization regardless if treatment kit is used or not.
ITT with screening blood eosinophil count $\geq 300$ cells/mm $^3$	All randomized participants with screening blood eosinophil count $\geq 300$ cells/mm $^3$ analyzed according to the treatment group allocated by randomization regardless if treatment kit is used or not.
Safety	All participants randomly assigned to study intervention and who take at least 1 dose of study intervention. Participants will be analyzed according to the intervention they actually received. Randomized participants for whom it is unclear whether they took the study medication will be included in the safety population as randomized. For participants who accidentally receive different study intervention from the planned, the actual intervention allocation for as-treated analysis will be the dupilumab group.

Population	Description
Pharmacokinetic (PK)	The PK population includes all participants in the safety population with at least 1 non-missing result for functional dupilumab concentration in serum after the first dose of the study intervention. Participants will be analyzed according to the intervention actually received.
Anti-drug antibody (ADA)	ADA population includes all participants in the safety population who have at least 1 non-missing result in the ADA assay after the first dose of the study intervention. Participants will be analyzed according to the intervention actually received.

ADA: anti-drug antibody; ICF: informed consent form; IRT: interactive response technology; ITT: intent-to-treat; PK: pharmacokinetic

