## 3.6 SAFETY ANALYSES

All safety analyses will be performed on the safety population as defined in [Section 2](#), unless otherwise specified, using the following common rules:

- The analysis of the safety variables will be essentially descriptive, and no testing is planned.
- Safety data in participants who do not belong to the safety population (eg, exposed but not randomized) will be provided.

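### The as-treated rule in the Safety row counts a participant randomised to dupilumab who received only placebo as dupilumab, against the general rule in the same row

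*SAP*

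**What the plan says.** The Safety row of SAP Table 3 starts with a general rule: "Participants will be analyzed according to the intervention they actually received". A later sentence in the row deals with dosing errors: "For participants who accidentally receive different study intervention from the planned, the actual intervention allocation for as-treated analysis will be the dupilumab group". Protocol Table 5 has the same rule in its Safety row, ending "the actual intervention allocation for as-treated analysis will be the dupilumab group", so this is not a slip confined to the SAP.

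The text below SAP Table 3 has a separate rule for mixed exposure: "For participants receiving more than one study intervention during the study, the intervention group for as-treated analyses will be the dupilumab group".

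The PK and ADA rows of SAP Table 3 take their members from the safety population but state their own grouping rule: "Participants will be analyzed according to the intervention actually received". Neither row assigns anyone to dupilumab by default, and the protocol's PK and ADA rows read the same way.

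SAP 3.6 opens with "All safety analyses will be performed on the safety population as defined in" Section 2, so the Safety-row grouping governs the adverse event, laboratory and vital-sign tables unless a section says otherwise.

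**The concern.** The dosing-error sentence is sound when dupilumab reached someone who was meant to have placebo, and when a participant received both products. It fails in the opposite direction. If a participant allocated to dupilumab was given placebo at every dose taken, the sentence still names dupilumab as the actual allocation. The general rule in the same row says placebo, and nothing states which sentence prevails. A programmer would normally let the specific rule override the general one, and here the specific rule gives the wrong group.

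At stake is the accuracy of the descriptive safety comparison. A participant never exposed to the drug would enter the dupilumab denominators, and any event that this participant had on placebo would be shown under dupilumab. Because the PK and ADA rows follow actual receipt, the same participant could also change group between tables in one report.

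**Working it through.** There is no figure in the plan to reproduce; the point rests on the wording of a rule. Two checks follow.

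**1. Apply the rule to every case.** The design has two arms: "Approximately 70 adult participants will be randomized 1:1 (approximately 35 participants per arm) into 2 treatment groups as follows" (protocol 4.1). Cross the planned arm with what was received. By exposure, any dupilumab dose means dupilumab, and placebo at every dose means placebo.

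| Planned | Received | Dosing-error sentence, taken literally | By exposure | Agree? |
|---|---|---|---|---|
| Dupilumab | Dupilumab only | Dupilumab (no error) | Dupilumab | Yes |
| Dupilumab | Placebo only | Dupilumab | Placebo | **No** |
| Dupilumab | Both | Dupilumab | Dupilumab | Yes |
| Placebo | Placebo only | Placebo (no error) | Placebo | Yes |
| Placebo | Dupilumab only | Dupilumab | Dupilumab | Yes |
| Placebo | Both | Dupilumab | Dupilumab | Yes |

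Five of the six agree. The mixed-exposure rule below Table 3 settles the two rows marked Both. It does not reach the failing row, where only one intervention was received.

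**2. Size of the effect on an incidence.** Inputs: a dupilumab denominator of 35 (protocol 4.1) and k misassigned placebo-only participants within it. The true event proportions, p on dupilumab and q on placebo, are assumptions, and so is k, since the documents give no dosing-error rate.

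Expected displayed incidence = ((35 − k)·p + k·q) / 35

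Relative change = −(k/35)·(1 − q/p)

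- With q = 0 and k = 1, the factor is 34/35 = 97.1%, a fall of 1/35 = 2.9% of the true value. For p = 20%: (34 × 0.20)/35 = 6.80/35 = 19.4%.
- With q = 5%, p = 20% and k = 1: (34 × 0.20 + 0.05)/35 = 6.85/35 = 19.6%, a fall of (1/35) × (1 − 0.25) = 2.1% of the true value.
- With q = p the expected change is zero.

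| k | p = 20%, q = 0 | p = 20%, q = 5% |
|---|---|---|
| 1 | 19.4% | 19.6% |
| 2 | 18.9% | 19.1% |
| 3 | 18.3% | 18.7% |

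These are expectations. If the misassigned participant happens to have the event, the displayed dupilumab count rises by one.

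**The case against.** **The sentence may mean less than it says.** It follows the general rule in the same row, and the text below Table 3 restates the as-treated rule in terms of more than one intervention. Read together, the dosing-error sentence could be loose wording of the mixed-exposure rule, which is sound. That is a plausible account of the intent. It does not change what the sentence says: a participant who received only placebo instead of dupilumab did accidentally receive a different intervention from the planned one.

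**It may be deliberately conservative.** Counting any dupilumab exposure as dupilumab is conservative. Counting a participant with none is not, because it tends to lower the incidence of drug-caused events in that group.

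**The case is rare.** This stands. Kits are allocated through the IRT, and an isolated kit error in a participant who continues treatment produces mixed exposure, which is handled correctly. The failing case needs placebo at every dose taken. It does not need months of errors, though: one dose is enough to enter the safety population, so a single wrong kit followed by discontinuation would suffice. Safety analyses are descriptive with no testing, and critical and major protocol deviations are summarised.

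**Stronger readings to avoid.** A reader might infer that the error carries into the PK and ADA results: a placebo-only participant given half the LLOQ rather than 0, lower mean troughs and a diluted ADA incidence. The documents do not support this. Drawing members from the safety population settles who is in the PK and ADA sets, not the group in which they are analysed, and both rows group by actual receipt. SAP 3.7.1.1 reserves half the LLOQ for drug-treated participants. Nor does the 2.9% apply to every incidence; it needs an event that is absent on placebo.

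**Conclusion.** The point holds, as a minor error confined to the Safety row. As written, the rule gives the wrong group in one of six planned-by-received combinations, contradicts the general rule beside it, and can split one participant between dupilumab for safety and placebo for PK and ADA.

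Per affected participant, the expected loss is at most about 2.9% of a dupilumab incidence when the event does not occur on placebo, and less when it occurs there at a lower rate. This assumes a denominator of about 35. The number of affected participants is unknown and may well be zero.

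The primary LMK analysis (SAP 3.2.2) and the secondary efficacy comparisons (SAP 3.3.2) use ITT populations grouped by randomised arm and are unaffected.

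**What to change.** In the Safety row of SAP Table 3, do one of the following:

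- Limit the dosing-error sentence by exposure. For example: Participants who received at least one dose of dupilumab are analysed in the dupilumab group; participants who received only placebo are analysed in the placebo group.
- Delete the sentence and rely on the general rule in the row plus the mixed-exposure rule below the table.

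Either choice agrees with exposure in all six combinations and keeps the conservative treatment of mixed exposure. The PK and ADA rows need no change.

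The SAP edit is one sentence and should be made before unblinding, so that no choice is left to be made once a case is known. Protocol Table 5 needs the same edit. Because that changes the protocol, it can be aligned at the next amendment; the point does not justify an amendment of its own.

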## 6.3 MEASURES TO MINIMIZE BIAS: RANDOMIZATION AND BLINDING

The randomized intervention kit number list is generated centrally by Sanofi, and IMPs are packaged in accordance with this list. The randomization and intervention allocation are performed centrally by IRT. The IRT generates the participant randomization list and allocates the intervention number and the corresponding intervention kits to the participants according to it. Before the study is initiated, the log-in information and directions for the IRT will be provided to each site.

Participants will be randomized in a 1:1 ratio treatment arm described in [Table 2](#).

Randomization will be stratified by screening blood eosinophil count ( $\geq 300$  cells/mm $^3$  or  $< 300$  cells/mm $^3$ ), background INCS use (yes or no) and region.

At Screening (Visit 1), the Investigator or designee will contact the IRT to receive the participant number. If a participant who had previously failed screening is approached for re-screening, a new ICF must be signed. In such case, a new participant number will be assigned by IRT.

A randomized participant is defined as a participant who has been allocated to a randomized intervention regardless of whether the treatment was administered or not (ie, participant registered by the IRT). A participant cannot be randomized more than once in the study.

Study intervention will be dispensed at the study visits summarized in the SoA ([Section 1.3](#)). Returned study intervention should not be re-dispensed to the participants.

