**Table 9 - Time window for safety endpoints**

Analysis visit	Target day	Time windows for		
		Vital signs	Laboratory (hematology, chemistry, urinalysis)	Urine pregnancy
Screening	-28 to -14	<-14	<-14	
Baseline	1	-14-1-	-14-1-	14-1-
Week 2	15	1*-49		
Week 4	29			1*-42
Week 8	57			43-70
Week 12	85	50-126	1*-126	71-98
Week 16	113			99-126
Week 20	141			127-154
Week 24	169	127-224	127-224	155-182
Week 28	197			183-210
Week 32	225			211-238
Week 36	253			239-266
Week 40	281	225-322	225-322	267-294
Week 44	309			295-322
Week 48	337			323-350
Week 52	365	>322	>322	>350

1:: up to 1st dose date/time; 1+: after 1st dose date/time;

For the efficacy assessment, the reference date for the derivation of relative days of events or findings will be the randomization day. If a participant receives IMP prior to the randomization by mistake, the reference date of efficacy assessment will be the date of the first IMP administration for that participant. For the primary analyses, all available values of scheduled measurements will be assigned to the appropriate visit window according to [Table 10](#). In the event of multiple measurements of the same test in the same window, the one closest to the targeted visit date will be used for the by-visit summary. If they are at the same number of days away from the target day, the latest one will be used.

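### SAP Section 2 removes a participant dosed before randomisation from every analysis population, while SAP 5.4 and the population definitions in Table 3 would keep that participant

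*SAP*

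**What the plan says.** Four parts of the documents bear on a participant who is given study drug first and randomised afterwards.

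- **SAP Section 2, text below Table 3:** "Participants exposed to study intervention before or without being randomized will not be considered randomized and will not be included in any analysis population". The next sentence adds: "The safety experience of these participants will be reported separately".
- **SAP 5.4, efficacy analysis windows:** "If a participant receives IMP prior to the randomization by mistake, the reference date of efficacy assessment will be the date" of that participant's first administration. For everyone else the reference date is the day of randomisation.
- **SAP Table 3 and protocol Table 5, randomised population (same sentence in both):** "Participants treated without being randomized will not be considered randomized and will not be included in any efficacy population".
- **General definitions:** Protocol 6.3 says "A randomized participant is defined as a participant who has been allocated to a randomized intervention regardless of whether the treatment was administered or not". ITT is "All randomized participants analyzed according to the treatment group allocated by randomization regardless if treatment kit is used or not". The safety set is "All participants randomly assigned to study intervention and who take at least 1 dose of study intervention". None of these depends on when the first dose was given.

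**The concern.** Section 2 widens the Table 3 exclusion by adding exposure before randomisation to exposure without it. Read literally, a participant dosed early and then allocated through the IRT is treated as not randomised, although the IRT holds a kit number for that person and Table 3 places them in the ITT and safety sets. SAP 5.4 assumes the opposite, because an efficacy reference date has no use for someone in no analysis population.

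What is at stake is the analysed number in the primary analysis and the denominators of the disposition, ITT and safety tables. The primary analysis is a mean in one small group, so a single participant is visible in it. A population rule meant for rare errors should give one answer before the data are unblinded.

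**Working it through.** **1. Does the wording conflict?** Take a participant dosed by mistake before the IRT transaction and then randomised.

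- Randomised population (Table 3, protocol Table 5, protocol 6.3): included, because a kit number is allocated and recorded in the IRT. The exclusion there covers only people never randomised.
- ITT (Table 3): included, as all randomised participants are.
- Safety (Table 3): included, as randomly assigned with at least one dose.
- SAP 5.4: efficacy data are windowed from first dose, so inclusion is presumed.
- SAP 3.1: efficacy baseline must be both no later than randomisation and before first dose. This fits keeping the participant.
- SAP Section 2 text: in no population.

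The word *before* in Section 2 adds something only for people who are later randomised, since those never randomised are already covered by *without*. The two rules therefore address the same person. SAP 3.9 lists only changes made by protocol amendments and does not mention the widening.

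**2. What does moving from efficacy populations to any analysis population add?** For people never randomised it adds almost nothing: the safety set already requires random assignment, and the PK and ADA sets lie within the safety set. The words *before or* are what change membership.

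**3. The plan's own precision figure.** Inputs from SAP Section 4 and 3.2.2: 15 dupilumab participants with eosinophils at or above 300, SD 5, 10% dropout, two-sided 95% interval from the t distribution. Half-width = t(0.975, n−1) × 5 / √n.

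- n = 15 × 0.9 = 13.5: 2.95 (normal approximation: 1.96 × 5 / √13.5 = 2.67). The stated figure of approximately less than 3 is reproduced.

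**4. Effect of losing one participant from that group.**

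- Share of the group: 1/15 = 6.7%.
- Half-width: from n = 14 to 13, 2.89 to 3.02; from n = 13 to 12, 3.02 to 3.18.
- Mean: if the lost value differs from the mean of the others by d, the mean of all n moves by d/n. With d = 5 (one SD), 5/15 = 0.33 and 5/13 = 0.38 LMK points.
- Share of all randomised participants: 1/70 = 1.4%.

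**5. Does keeping the participant work with the diary rules?** Not as they stand. Protocol 9.4.1 and SAP 3.1 average the diary over the 7 days before randomisation, and the diary text in SAP 5.4 makes the day of randomisation Day 1. If dosing precedes randomisation by k days (k up to 7), at most k of the 7 baseline days could follow the first dose. For dosing earlier on the same day, k = 0 and there is no effect. The sTSS baseline needs its own line for these participants.

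**The case against.** The strongest reply is that this is a drafting inconsistency about an event that should hardly occur. The IRT allocates kits, and the investigator or delegate gives the first dose on site at Visit 2, so early dosing would mean using a kit not yet allocated. The documents report no such case. An affected participant would fall in the primary dupilumab group only about 15 times in 70 (21%), and no hypothesis is tested. All of that stands, and it limits the size of the point.

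Three stronger readings are tempting, and the documents do not support them.

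- A reader might infer that the protocol expressly keeps such a participant. It does not mention dosing before randomisation; it keeps them only through general definitions. The explicit conflict is inside the SAP.
- A reader might infer that safety information would be lost. Section 2 reports it separately, SAP 3.6 provides safety data for people outside the safety set, and SAP 5.2 counts those exposed and not randomised. The denominators would change; the data would not disappear.
- A reader might infer a biased comparison, or a population chosen after the data are seen. Early exposure is fixed before allocation, so an exclusion applied alike to both arms is not post-randomisation selection. Nothing suggests that the choice would be made with knowledge of results.

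It can also be said that Section 2 is the populations section and should govern over a date convention in an appendix, so that deleting the 5.4 rule and declaring the departure in SAP 3.9 would serve. That would give one answer, but it would keep an exception to the SAP's own ITT and safety definitions. The SAP states no precedence between the two sections.

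**Conclusion.** The point holds as an internal contradiction in the SAP that should be settled before database lock. Followed literally, Section 2 takes a randomised and treated participant out of the randomised, ITT and safety sets, against Table 3 and against the purpose of the rule in 5.4. Its practical weight is small and depends on an affected participant actually occurring. The 6.7% and the half-width changes further assume that this participant is in the dupilumab arm with eosinophils at or above 300, that SD 5 holds, and that 12 to 14 participants are evaluable. The shift of 0.33 to 0.38 points assumes a value one SD from the others. The exclusion of people never randomised is sound and is not questioned.

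**What to change.** Before database lock and unblinding:

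- In the SAP Section 2 text, delete *before or*, so that only participants exposed without ever being randomised are excluded. State that a participant dosed early and then randomised stays in the randomised and ITT sets as randomised, and in the safety set as treated.
- Keep the first-dose reference date already in SAP 5.4 for these participants. For them alone, tie the diary baseline in SAP 3.1 and diary Day 1 in SAP 5.4 to first dose, so that post-dose days do not enter the sTSS baseline.
- Report the sequence error as a protocol deviation.
- Declare the diary exception in SAP 3.9, because it departs slightly from the baseline wording in protocol 9.4.1.

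The cost is two or three SAP sentences and that small exception. No new data are needed, and no planned figure changes.
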